## **4. STUDY CONDUCT**

The following section outlines the study implementation plan, details on the study measures that will be collected as part of it are provided in Section 5.

### **4.1 Study Plan**

This study has been subject to an internal review according to AstraZeneca standard procedures.

Concomitant treatments, other than anti-cancer treatments, should be taken according to local medical practice. There are no restrictions on concomitant use in this study except per exclusion criteria. However, it is advised that those medical products and other products known to have interactions with AZD9291 should be avoided (see [Appendix B](#)).

The latest version of the IB and any subsequent updates will be supplied to the investigator. Investigators need to become familiar with the content of the IB and appendices associated with this protocol.

[Table 4](#) below outlines data collection measures that are considered for this study:

**Table 4 Study Plan**

	Screening/ Enrolment visit		Treatment visit	Treatment Discontinuation	30 day follow up (c)	Progression Follow-up (e)	Survival follow up (g)
	-28 days	Day 1	(every 6 weeks)			(every 6 weeks)	(every 6 weeks)
Windows (days)			+/- 7 days	+/- 7 days	+/- 7 days	+/- 7 days	+/- 7 days
Informed Consent	X						
Inclusion/Exclusion criteria check	X						
Complete enrolment form	X						
Confirm T790M mutation	X (d)						
Patient demographics	X						
Medical history	X						
Disease characteristics	X						
Cancer treatment history	X						
Concomitant medications	X	X	X	X			
Complete blood count	X		If clinically indicated or per institutional standard of care	If clinically indicated or per institutional standard of care			
Biochemistry in blood and urine	X		If clinically indicated or per institutional standard of care	If clinically indicated or per institutional standard of care			
Pregnancy test	X (h)						
Physical examination	X			X			
WHO Performance status	X		X	X			
Weight	X		X	X			
ECG recording	X		If clinically indicated or per institutional standard of care	If clinically indicated or per institutional standard of care			
Visual test (slit-lamp)	X		If clinically indicated or per institutional standard of care	If clinically indicated or per institutional standard of care			
Dispense AZD9291 (IVRS/IWRS)		X AZD9291 start-dose	X AZD9291 re-supply				
AZD9291 dosing (daily): - current dose; dose adjustment;			X				

	Screening/ Enrolment visit		Treatment visit	Treatment Discontinuation	30 day follow up (c)	Progression Follow-up (e)	Survival follow up (g)
interruption/discontinuation reason for change							
Drug accountability			X				
Investigator-reported efficacy			X	X		X	
SAE, including overdose and pregnancy reporting (a)(f)		X	X	X	X	X	
Adverse event of special interest (b) AEs leading to dose modification including drug discontinuation			X	X	X	X	
Reason for withdrawal				X			
Survival status							X

- (a) Following AZD9291 discontinuation, SAEs considered related to study procedures should continue to be collected until disease progression
- (b) ILD/pneumonitis-like event; cardiac event (see section 6.6.1 and 6.6.2).
- (c) A 30 day post last dose follow up contact (visit or by telephone) should be made with the subject to collect new SAEs, andAESI and to follow up on any ongoing SAEs andAESI.
- (d) Before initiating treatment with AZD9291 the T790M mutation status after progression needs to be known. T790M mutation test may have been done per routine practice earlier than 28 days prior to day 1 as long as this was obtained following the progression on prior TKI therapy (patients may also have received additional lines of treatment).
- (e) For subjects withdrawn from treatment but who had not progressed at the time of AZD9291 discontinuation. Follow up to be performed every 6 weeks ( $\pm 1$  week) relative to the date of enrolment until end of study (including survival follow-up period).
- (f) Pregnancy test to be performed in accordance with local standards
- (g) Survival status to be performed every 6 weeks ( $\pm 1$  week) relative to the date of enrolment until end of study

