5. Patient visits (e.g. physical exam, laboratory tests, etc.) must be performed according to the institutional standard of care and investigator's best medical judgment. AZD9291 re-supply must always be preceded by a treatment visit per [Table 4](#). Additionally, at each visit:

- a. Drug accountability must be documented in the case report form (CRF) and necessary paper logs.
- b. Patient needs to be screened for reportable safety events outlined in [Section 6](#)
- c. Investigator-reported efficacy measures described in [Section 5](#) needs to be documented in the CRF
- d. Investigators are required to assess the patient's performance status and confirm that the patient continues to be deriving benefit from AZD9291 at the time of study drug re-supply.
- e. If a patient withdraws from the treatment and/or completely from the study, the investigator will record the reason for withdrawal

**\*\*Please note that if the reason for withdrawal is an event meeting the definition of SAE, it must be recorded in both the safety and clinical forms\*\***

- f. For patients lost to follow-up, every reasonable effort must be made to establish the survival status and document this in the CRF
6. As an investigational drug, AZD9291 must be stored appropriately and dispensed from a secure storage area (or site pharmacy). Study sites are required to maintain accountability logs for drug receipt, dispensation, destruction and return (as applicable per local regulations).
- a. AZD9291 may only be used for the specific patient enrolled into the study.
7. Patients must be followed through the designated follow-up period (30 days post last dose of AZD9291 study medication) to collect SAEs occurring during this period and other required reporting per Section 6 and follow-up on any ongoing SAEs.

Consenting patients who do not fulfil the eligibility criteria must not be enrolled (dosed) into the study and will be discontinued. They will be considered screening failures and only demography data, reason for discontinuation will be recorded. Supporting safety information can be collected in case of SAE, if applicable.

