### **6.2 Definition of serious adverse events**

An SAE is an event occurring from the time the patient signs informed consent (as per local regulations) through the end of the post-treatment follow-up visit (30 days post-last dose) or

until disease progression, whichever is the latest, which fulfils one or more of the following criteria:

- Results in death
- Is immediately life-threatening
- Requires in-patient hospitalization or prolongation of existing hospitalization
- Results in persistent or significant disability/incapacity or substantial disruption of the ability to conduct normal life functions
- Is a congenital abnormality or birth defect
- Is an important medical event that may jeopardize the patient or may require medical intervention to prevent one of the outcomes listed above.

For further guidance on the definition of an SAE, see [Appendix A](#) to the study protocol.

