## 6.3 Reporting of serious adverse events

All SAEs must be reported through the completion and submission of the SAE report form, from the time of signature of informed consent through 30 days post-last dose, whether or not considered causally related to AZD9291.

If any SAE occurs in the timeframe mentioned above, then the investigator or other site personnel must inform the appropriate AstraZeneca representatives within one day i.e., immediately but **no later than 24 hours** of when he or she becomes aware of it.

The designated AstraZeneca representative will work with the investigator to ensure that all the necessary information is provided to the AstraZeneca Patient Safety data entry site **within 1 calendar day** of initial receipt for fatal and life threatening events **and within 5 calendar days** of initial receipt for all other SAEs.

For fatal or life-threatening adverse events where important or relevant information is missing, active follow-up is undertaken immediately. Investigator or other site personnel must inform AstraZeneca representatives of any follow-up information on a previously reported SAE within one calendar day, i.e., immediately but **no later than 24 hours** of when he or she becomes aware of it.

The investigator or other study site personnel must report SAEs to the appropriate AstraZeneca representative through the completion and submission of the AstraZeneca SAE report form.

The AstraZeneca representative will advise the investigator/study site personnel how to proceed.

The reference document for definition of expectedness/listedness is the IB for the AstraZeneca drug AZD9291.

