### 3.2.1 SAEs

SAEs will be collected throughout the study, from the date of first dose of AZD9291 until 30 days after the last dose of study medication or until disease progression, whichever is the latest. The latest version of the Medical Dictionary for Regulatory Activities (MedDRA) will be used to code the SAEs. SAEs will be graded according to the National Cancer Institute Common Terminology Criteria for AEs (CTCAE Version 4.03).

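### Table 4 lets the 30-day safety contact fall up to 7 days early, leaving a small gap in scheduled SAE and AESI enquiry for patients who had already progressed

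*Protocol*

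**What the plan says.** **The contact.** Footnote (c) to Table 4 of the protocol states: "A 30 day post last dose follow up contact (visit or by telephone) should be made with the subject to collect new SAEs". It adds AESIs and the follow-up of ongoing events. The windows row of the table gives this column +/- 7 days, the same as the other post-baseline columns.

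**What comes after it.** Two later columns exist.
- Progression Follow-up has marks in the SAE and AESI rows. Footnote (e) restricts it: "For subjects withdrawn from treatment but who had not progressed at the time of AZD9291 discontinuation".
- Survival follow up has one mark, survival status. Footnote (g): "Survival status to be performed every 6 weeks".

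**What the protocol text requires.**
- Section 4.1, item 7: "Patients must be followed through the designated follow-up period (30 days post last dose of AZD9291 study medication) to collect SAEs". It also refers to other reporting required under Section 6.
- Section 6.3 requires all SAEs to be reported "from the time of signature of informed consent through 30 days post-last dose, whether or not considered causally related to AZD9291".
- Section 4.4 requires safety follow-up to 30 days after the last dose for patients who withdraw and agree to it.
- Section 6.2 runs the SAE period "through the end of the post-treatment follow-up visit (30 days post-last dose) or" to progression, if that is later.

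**What is analysed.** Protocol Section 9.4.3 includes adverse events up to 30 days after the last dose, or to progression if later. SAP Section 3.2.1 collects SAEs "until 30 days after the last dose of study medication or until disease progression, whichever is the latest". SAP Section 4.2.8 tabulates SAEs that start up to 30 days after therapy stops. For a patient who had progressed before stopping, all three limits come to day 30.

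**The concern.** The contact meant to close the 30-day safety period may be made before that period ends. A patient who had not progressed will be asked again under Progression Follow-up. A patient who had progressed has no later planned contact at which SAEs or AESIs are asked about. If the contact is early, the remaining days to day 30 depend on the event reaching the site by some other route.

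Safety is part of the primary objective, and progression is a listed reason for stopping treatment (Section 4.3), so this group is not marginal. Any loss works in one direction: it can only lower the counts of events after the last dose.

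**Working it through.** **1. The window.** Nominal day 30, window +/- 7 days (Table 4): 30 - 7 = 23 and 30 + 7 = 37. There are 15 permitted contact days.

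**2. Days without a scheduled enquiry in a progressed patient.** For contact on day d, the gap is max(0, 30 - d).

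| Contact day | 23 | 24 | 25 | 26 | 27 | 28 | 29 | 30-37 |
|---|---|---|---|---|---|---|---|---|
| Gap (days) | 7 | 6 | 5 | 4 | 3 | 2 | 1 | 0 |

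- Worst case: 7/30 = 23.3% of the period, for a contact on exactly day 23.
- The documents give no distribution of contact days. If they are spread evenly over the 15 days (assumption), 7/15 = 46.7% are early. The mean gap is (7+6+5+4+3+2+1)/15 = 28/15 = 1.87 days, which is 6.2% of 30 days.

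**3. Which events another rule covers between an early contact and day 30.**

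| Event in a progressed patient | Duty in the text | Scheduled enquiry after an early contact |
|---|---|---|
| Death | Section 6.2.1 (reporting to day 30) | Yes, survival status every 6 weeks |
| Non-fatal SAE | Section 4.1 item 7; Section 6.3; Section 4.4 on withdrawal | None |
| Non-serious QTc event | Section 6.6.2: QTcF above 470 ms reportable at any point in the study | None |
| Non-serious ILD/pneumonitis-like event | Item 7, by reference to Section 6; the opening of Section 6 points back to Table 4 | None |

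The last row is the weakest. The reference chain ends at the table that contains the early window.

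**4. Approximate size for SAEs.** Inputs:
- 3500 patients (protocol synopsis).
- 70% stopping after progression (assumption; the documents give no figure).
- Mean gap 28/15 days (assumption in step 2).
- SAEs in 10.5% of patients, 21/201, in the phase II extension (protocol Section 1.4.2.2), over about 135 days. The 135 days is an assumption: 4.5 months of 30 days, the midpoint of the 3-to-6-month exposure band that held just over half of those patients.

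Patient-days without scheduled enquiry: 3500 x 0.70 x 28/15 = 2450 x 1.867 = 4573.

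Rate: 0.105/135 = 0.00078 per patient-day.

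SAEs falling in the gap: 4573 x 0.105/135 = 3.6, or about 4. Set against 3500 patients this is about 0.1 percentage point.

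Range, changing one assumption at a time:
- Exposure of 3 or 6 months (91.3 or 182.6 days) instead of 135 days: 5.3 or 2.6 SAEs.
- All 3500 patients stopping after progression: 3.6/0.70 = 5.1.
- Every contact on day 30 or later: 0.
- Every contact on exactly day 23: 2450 x 7 x 0.105/135 = 13.3. Nothing in the documents suggests this pattern.

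All these figures treat every SAE in the gap as missed, so each is a ceiling for its scenario. The documents give no rate for non-serious AESIs after stopping, so no figure can be given for them.

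**5. After the change.** With a window of 0/+7 the permitted days are 30-37, and the gap is 0 for each of them.

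**The case against.** The strongest reply is that the text already requires what the table leaves open. Section 4.1 item 7 is mandatory and carries no 7-day allowance, Section 6.3 requires SAE reporting through day 30, and Section 4.4 does the same for withdrawn patients who agree. A call on day 23 meets the visit window but does not discharge item 7. This stands. A reader might infer from Table 4 that SAEs on days 24-30 are never collected in progressed patients; the documents do not support that.

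What the reply leaves untouched is that a duty to report is not a planned enquiry. A non-fatal SAE treated at another hospital on day 27 reaches the site only if someone tells it. Section 6.2 also names the follow-up visit as an end of the SAE period, so a site could read an early contact as closing it. The duty in Section 6.3 covers SAEs only.

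A second reply concerns size, and it also stands. The full 7-day gap needs a contact on exactly day 23, and footnote (c) sets day 30 as the target. Patients who move to commercial supply at reimbursement are outside the affected group, so 70% may be too high. SAP Section 4.2.8 counts a repeated SAE once per patient, and a patient with an earlier SAE does not change the percentage with at least one. The analyses are descriptive.

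Two further inferences go too far. One is that the reported SAE and AESI percentages are therefore too low: under-ascertainment is possible but not shown. The other is that the safety tables assume every patient was observed to day 30: they define which events are included and use patient counts, with no person-time denominator.

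**Conclusion.** The Table 4 window does not agree with the day-30 period used in protocol Sections 4.1 (item 7), 6.2, 6.3 and 9.4.3 and in SAP Sections 3.2.1 and 4.2.8. For patients who had progressed before stopping, a compliant contact on days 23-29 leaves 1-7 days without a scheduled SAE or AESI enquiry. Because separate SAE duties run to day 30, the consequence is possible slight under-ascertainment, mainly of non-serious AESIs and of non-fatal SAEs treated elsewhere.

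The gap and its 7-day limit follow from the documents alone. The mean gap of about 1.9 days rests on the even spread. The figure of at most about 4 SAEs rests on that spread, the 70% share, the 135 days of exposure and an on-treatment rate carried over to the days after stopping. A reader might expect a higher rate after progression, but the documents give none, so no larger estimate on that ground is justified. Severity is minor.

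**What to change.** In Table 4, change the window of the 30-day follow-up column from +/- 7 days to 0/+7 days, so that contact falls on days 30-37. Keep day 30 as the cut-off for events in the tables. Table 4 then agrees with the sections listed in the conclusion.

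For contacts already made before day 30 in progressed patients, ask about SAEs and AESIs up to day 30 at the next 6-weekly survival contact.

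The cost is one table cell and one line in the CRF instructions. The downside is that some calls take place up to a week later.

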### **Patient enrolment:**

1. The investigator will determine patient eligibility based on criteria outlined in Section 3.1 and 3.2.
2. The investigator will inform the patients about the study, AZD9291, the potential benefits and risks, AE reporting, as well as other information collected within the scope of the study. Subsequently, the investigator will obtain signed informed consent from the potential patient or legally acceptable representative, as appropriate per local regulations

Each patient will be assigned a unique identifier through the Interactive Voice Response System (IVRS)/ Interactive Web Response System (IWRS) in the following format ECCNN3XX: CC being the country code, NN being the centre number and 3XX being the subject enrolment code at the centre into the study.

In the event of a patient having an SAE delaying the start of treatment, the screening assessments will need to be performed within 28 days prior to treatment and entered in the CRF in the extended screening visit.

If a subject withdraws from participation in the study, then his/her enrolment code cannot be reused.

3. The investigator will provide a completed enrolment form

The laboratory report describing the test and specimen used to confirm the presence of T790M mutation must be available on site. Before initiating treatment with AZD9291 the tumor's T790M mutation status after progression with an EGFR TKI needs to be known. The test will be performed via a local laboratory wherever possible, and always in an accredited, certified or quality assured clinical laboratory as required by country-specific guidelines, using an appropriately validated test. If T790M mutation status is not known, a new sample following progression on the latest line of therapy may need to be obtained to be sent to a suitable local laboratory or a designated central laboratory (\*) for analysis. In that circumstance the patient will be requested to provide consent prior to carrying out this procedure.

(\*) Note: No other genetic tests will be performed other than EGFR mutation test and samples will not be retained by the central lab if a central lab needs to be used. The samples provided will be destroyed at the end of the study or returned upon request as per the Laboratory Manual of the designated central laboratory.

4. The study site must receive enrolment confirmation for each patient from AstraZeneca (or designee) prior to drug dispensation

5. Patient visits (e.g. physical exam, laboratory tests, etc.) must be performed according to the institutional standard of care and investigator's best medical judgment. AZD9291 re-supply must always be preceded by a treatment visit per [Table 4](#). Additionally, at each visit:

- a. Drug accountability must be documented in the case report form (CRF) and necessary paper logs.
- b. Patient needs to be screened for reportable safety events outlined in [Section 6](#)
- c. Investigator-reported efficacy measures described in [Section 5](#) needs to be documented in the CRF
- d. Investigators are required to assess the patient's performance status and confirm that the patient continues to be deriving benefit from AZD9291 at the time of study drug re-supply.
- e. If a patient withdraws from the treatment and/or completely from the study, the investigator will record the reason for withdrawal

**\*\*Please note that if the reason for withdrawal is an event meeting the definition of SAE, it must be recorded in both the safety and clinical forms\*\***

- f. For patients lost to follow-up, every reasonable effort must be made to establish the survival status and document this in the CRF
6. As an investigational drug, AZD9291 must be stored appropriately and dispensed from a secure storage area (or site pharmacy). Study sites are required to maintain accountability logs for drug receipt, dispensation, destruction and return (as applicable per local regulations).
- a. AZD9291 may only be used for the specific patient enrolled into the study.
7. Patients must be followed through the designated follow-up period (30 days post last dose of AZD9291 study medication) to collect SAEs occurring during this period and other required reporting per Section 6 and follow-up on any ongoing SAEs.

Consenting patients who do not fulfil the eligibility criteria must not be enrolled (dosed) into the study and will be discontinued. They will be considered screening failures and only demography data, reason for discontinuation will be recorded. Supporting safety information can be collected in case of SAE, if applicable.

## **4.2 Restrictions**

The following restrictions apply while the patient is receiving AZD9291 and for the specified times before and after:

1. Females of childbearing potential must use reliable methods of contraception from the time of screening until 3 months after discontinuing AZD9291. Acceptable methods of contraception include true abstinence, when this is in line with the preferred and usual lifestyle of the subject. [Periodic abstinence (e.g., calendar, ovulation, symptothermal, post-ovulation methods), declaration of abstinence for the duration of a trial, and withdrawal are not acceptable methods of contraception], tubal ligation, hormonal contraceptives that are not prone to drug-drug interactions (e.g., IUS Levonorgestrel Intra Uterine System, Medroxyprogesterone injections), copper-banded intra-uterine devices, and vasectomized partner. All hormonal methods of contraception should be used in combination with the use of a condom by their male sexual partner(s) for intercourse.
2. Male patients must be asked to use barrier contraceptives (i.e., by use of condoms) during sex with all of their female partners during the trial and for a period of 6 months. Patients should not father a child for 6 months after completion of AZD9291 treatment. Patients must refrain from donating sperm from the start of dosing until 6 months after discontinuing AZD9291 treatment. If male patients wish to father children they should be advised to arrange for freezing of sperm samples prior to the start of AZD9291 treatment.
3. If medically feasible, patients taking regular medication, with the exception of potent inducers of CYP3A4 (see [Appendix B](#)), should be maintained on it throughout the study

period (30 days post-last dose). Patients taking concomitant medications whose disposition is dependent upon CYP3A4 and breast cancer resistance protein and which have a narrow therapeutic index should be closely monitored for signs of changed tolerability as a result of increased exposure of the concomitant medication whilst receiving AZD9291. Patients taking concomitant medications whose disposition is dependent upon CYP3A4, CYP1A2, CYP2C or p-glycoprotein and which have a narrow therapeutic index should be closely monitored for reduction in therapeutic activity as a result of the reduced exposure of the concomitant medication while receiving AZD9291. Guidance on medications to avoid, medications that require close monitoring and on washout periods is provided (see [Appendix B](#)).

Up to 3-fold increase in exposure may occur in statin exposure when co-administered with AZD9291. It is recommended that the starting and maintenance dose of statins should be as low as possible and should be guided by the statin prescribing information.

Patients taking warfarin should be monitored regularly for changes in prothrombin time or international normalized ratio.

Patients who wear contact lenses must discontinue wearing their lenses if they have any mild to moderate eye symptoms (CTCAE grade  $\leq 2$ ) while receiving treatment with AZD9291 until at least one week after symptoms have resolved. If a patient has a recurrence of eye symptoms or experiences any severe (CTCAE grade  $\geq 3$ ) ocular events, they must discontinue wearing their contact lenses until at least one week after treatment with AZD9291 is permanently discontinued. Patients must not use any eye drops or ointment for treatment of eye symptoms, unless agreed to by a study doctor, at any time during the study until 1 week after AZD9291 has been permanently discontinued. Patients must consult their investigator promptly if they have any concerns.

